#### Study B (years two and three of mortality contingency study)

1. Sample size considerations are the same as in Study A (year 1).
  - a. Assuming communities of size 668 with approximately 17% in the target age range, an effect size of 20%, 10% loss to follow-up per year, 2% mortality per year, and a CV of 0.51, 312 communities per arm provides approximately 87% power (see MORDOR Phase I SAP for details).
  - b. Updating based on data from Phase I (Niger), we find the following. Assuming the observed CV of 0.34, a death rate of 2% per year results in approximately 80% power to detect a 17% effect. A death rate of 2.5% per year (and a CV of 0.34) result in approximately 80% power to detect a 15.5% effect size.
2. The primary prespecified analysis will contrast the rerandomized placebo arm with the rerandomized azithromycin arm. This will be conducted with negative binomial regression, using a two-sided  $\alpha$  of 0.05 and a permutation test by randomization arm.
3. Supplementary analyses will control for prior history (original randomization arm).
4. Longitudinal analysis for communities who always received azithromycin will be reported.
5. We will compare all four groups for the last year of data (two histories by two final treatments).

6. Additional analyses by the same age groups as before and by phase will be reported.
7. Models of timing, seasonality, and geography will be reported as secondary analysis.

Morbidity Study. Analysis of morbidity communities will follow the exact template as Stage I. Primary prespecified analyses will be two-sided, at an alpha of 0.05. However, the morbidity communities are still receiving placebo. Note that we will report the full follow-up at 48 months separately from the Stage 1 primary analyses. We will also look for secular effects longitudinally over the four years of the full study, as well as phases 5-8 separately.

1. Anthropometry: we will examine height and weight longitudinally, and WFH Z score secondarily. Please see the Stage 1 SAP for details.
2. Other analyses will include drug resistance and malaria, as in Stage 1.
3. Note that we do not do nares or conjunctiva swabs, conjunctival photos, or any swabs on 7-12 year olds in the contingency study.

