17.8 Contingency DSMC Committee

The MORDOR contingency study delivered open label azithromycin during the third year of the study to all participants. At the beginning of year 4, the communities were re-randomized to either placebo or azithromycin and a new DSMC committee was formed. This committee will follow the same charter as the original committee, with the exception of there being no plan to conduct an interim analysis and no futility or stopping rules. This DSMC committee is comprised of the following individuals:

[name] (chair) Infectious Disease Specialist, Prevention and Public Health Group University of California, San Francisco San Francisco, CA 94143 [contact] [contact]
[name] Professor, Epidemiology & Biostatistics University of California, Berkeley [name] [contact] [contact]
[name] Professor, Epidemiology & Biostatistics University of California, San Francisco San Francisco, CA 94143 [contact]

Chapter 18: Data Collection, Management, and Security

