## Introduction

This document (Statistical Analysis Plan, SAP) describes the planned analysis and reporting for the clinical trial, **Mortality Reduction after Oral Azithromycin**, Contingency Study, Years 3-4, Niger. It includes specifications for the statistical analyses and tables to be prepared for the interim and final Clinical Study Report. This study is a Phase IV clinical trial to compare methods to reduce childhood mortality using mass administration of azithromycin (Pfizer, CAS 83905-01-5) compared to placebo. The content of this Statistical Analysis Plan meets the requirements stated by the US Food and Drug Administration and conforms to the American Statistical Association's Ethical Guidelines.

The following documents were reviewed in preparation of this Statistical Analysis Plan:

- Mortality Reduction after Oral Azithromycin, Protocol
- Mortality Reduction after Oral Azithromycin, Statistical Analysis Plan
- Mortality Reduction after Oral Azithromycin, Manual of Operations
- ICH Guidance on Statistical Principles for Clinical Trials

The planned analyses described in this SAP will be included in future manuscripts. Exploratory analyses not necessarily identified in this Statistical Analysis Plan may be performed to support the analysis. Unplanned analyses not delineated in this Statistical Analysis Plan will be documented as such in the final Clinical Study Report and manuscripts.

This document will be reviewed prior to the enrollment of patients. All subsequent changes will be indicated by detailed change log in the Appendix.

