## 2 Design

Contingency study A. All communities in Niger will receive treatment at the conclusion of MORDOR Stage 1 (original study). Specifically, azithromycin communities will continue with azithromycin, and placebo communities will receive azithromycin at the 24 month visit (census number 5). Follow-up will occur at month 30 and month 36, providing one additional year of data.

Contingency study B. At the 36 month visit, rerandomization will occur, and half of communities will begin to receive placebo.

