## 3 Analysis

The primary outcome is mortality, analyzed in the same way as in MORDOR Stage I, i.e., present on an initial census, and absent on the next follow-up census due to death. Since the study has been extended, the same analytic template will be used for each visit, e.g. at 48, 54, and 60 months. Each visit that is conducted will be reported.

Study A:

1. Sample size considerations.
  - a. Assuming communities of size 668 with approximately 17% in the target age range, an effect size of 20%, 10% loss to follow-up per year, 2% mortality per year, and a CV of 0.51, 312 communities per arm provides approximately 87% power (see MORDOR Phase I SAP for details).
  - b. Updating based on data from Phase I (Niger), we find the following. Assuming the observed CV of 0.34, a death rate of 2% per year results in approximately 80% power to detect a 17% effect. A death rate of 2.5% per year (and a CV of 0.34) result in approximately 80% power to detect a 15.5% effect size.
2. Primary prespecified analysis: We propose to compare the former placebo arms with the former azithromycin arms, using negative binomial regression. Significance testing is two-sided with an alpha of 0.05, and will be based on permutation testing. (This analysis is identical in every way to the country subgroup analyses conducted in Stage 1). This is restricted to the period from 24 months to 36 months, covering two six-month study intervals.

3. We propose, as a prespecified secondary analysis, a longitudinal comparison of the original placebo communities. We propose to contrast the first four study intervals during which these communities received placebo, to the last two study intervals during which these communities received azithromycin. Analysis will be conducted using negative binomial regression, with a permutation P-value reported (two-sided,  $\alpha=0.05$ ). The community-randomized nature of the trial is thus taken into account.
4. Additional supplementary analyses will be distinguished from the two prespecified analyses above. In particular, the following will be reported:

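### Study B repeats Study A's one-year power figures, although its rerandomised follow-up runs two years, so its stated power and detectable effects are wrong (on the conservative side)

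*SAP*

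**What the plan says.** **Primary analysis.** SAP, Study B, item 2: "The primary prespecified analysis will contrast the rerandomized placebo arm with the rerandomized azithromycin arm". The item adds negative binomial regression, a two-sided 0.05 level and a permutation test. It names no months.

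**Period.** The section heading reads "Study B (years two and three of mortality contingency study". SAP section 2 (Design) gives the start: "At the 36 month visit, rerandomization will occur, and half of communities will begin to receive placebo". Protocol 17.8 agrees: "At the beginning of year 4, the communities were re-randomized to either placebo or azithromycin". The first contingency year is months 24-36, to which Study A's primary analysis is explicitly restricted. The second and third are therefore months 36-60.

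**Power.** Study B, item 1: "Sample size considerations are the same as in Study A (year 1"). The same figures then follow:
- (a) 312 communities per arm, community size 668 with about 17% in the age range, 2% mortality per year, CV 0.51, 10% loss per year, 20% effect: about 87% power.
- (b1) CV 0.34, 2% per year, 17% effect: about 80% power.
- (b2) CV 0.34, 2.5% per year, 15.5% effect: about 80% power.

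No follow-up length is given. For (a), the SAP refers to the Phase I SAP for details.

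**The concern.** The same power figures are given for a 12-month comparison (Study A) and for one that appears to last 24 months (Study B). With the same communities, annual death rates and CVs, doubling the follow-up roughly doubles the expected deaths per community and shrinks the Poisson part of the variance. One set of figures cannot hold for both.

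The effect size that Study B can detect is at stake. A reader who takes the SAP at its word would think Study B reaches 80% power only at a 17% or 15.5% effect, and would read a null result, or an effect of about 13%, against the wrong benchmark.

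**Working it through.** **Inputs** (SAP, Study B, item 1): c = 312 communities per arm; 668 x 0.17 = 113.56 children per community; scenarios (a), (b1) and (b2) as listed above; two-sided alpha 0.05.

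**Assumptions.** The SAP names no formula and does not say how loss enters. I used the standard formula for two rates in an unmatched cluster-randomised trial (Hayes-Bennett) and tried several loss rules.

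Power = Phi(z - 1.96), with

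z = sqrt[ (c - 1)(r0 - r1)^2 / ( (r0 + r1)/y + k^2 (r0^2 + r1^2) ) ]

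Here r0 is the control rate, r1 = r0(1 - effect), k the CV and y the child-years per community.

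**Step 1: reproduce the SAP's figures at 12 months.** With 0.9 retention, y = 113.56 x 0.9 = 102.2. For (a), r0 = 0.020 and r1 = 0.016:
- Poisson term: 0.036/102.2 = 0.000352
- between-community term: 0.51^2 x (0.0004 + 0.000256) = 0.000171
- z = sqrt(311 x 0.000016 / 0.000523) = 3.08, so power = Phi(1.12) = 87.0%

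The same steps give 81.9% for (b1) and 81.3% for (b2). All three are within 2 points of the stated 87/80/80%. A gamma-Poisson simulation gave 87.1%, 82.0% and 81.6%.

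**Step 2: change only the follow-up, to 24 months.** With flat 0.9 retention, y = 204.4. For (a) the Poisson term halves to 0.000176 and the between-community term stays at 0.000171. Then z = 3.79 and power = 96.6%.

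**Step 3: vary the loss rule.**

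| Follow-up and loss rule | y | (a) 20% | (b1) 17% | (b2) 15.5% |
|---|---|---|---|---|
| SAP as stated | not given | 87% | 80% | 80% |
| 12 months, 0.9 | 102.2 | 87.0% | 81.9% | 81.3% |
| 12 months, mid-interval | 107.9 | 88.1% | 83.5% | 82.9% |
| 12 months, no loss | 113.6 | 89.1% | 85.0% | 84.3% |
| 24 months, 0.81 throughout | 184.0 | 95.8% | 95.0% | 94.2% |
| 24 months, 0.9 then 0.81 | 194.2 | 96.2% | 95.7% | 94.9% |
| 24 months, 0.9 throughout | 204.4 | 96.6% | 96.2% | 95.5% |
| 24 months, no loss | 227.1 | 97.3% | 97.2% | 96.6% |

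Simulation at y = 204.4 gave 97.1%, 95.7% and 95.8%.

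**Step 4: solve for the effect detectable at the stated power (87/80/80%) over 24 months.**

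| Loss rule | (a) | (b1) | (b2) |
|---|---|---|---|
| SAP as stated | 20% | 17% | 15.5% |
| 0.81 throughout | 16.9% | 13.4% | 12.4% |
| 0.9 then 0.81 | 16.7% | 13.1% | 12.2% |
| 0.9 throughout | 16.5% | 12.9% | 12.0% |
| no loss | 16.1% | 12.5% | 11.6% |

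**Step 5: allow for dropout of communities.** With 280 rather than 312 per arm (my choice, for illustration) and y = 204.4, 24-month power is 94.8%, 94.3% and 93.3%, still well above the stated figures.

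**The case against.** **The 12-month fit is inferred.** The SAP gives no follow-up length for its power figures, and the Phase I SAP may set out a different formula or loss rule. With no loss, my 12-month values are 89/85/84% rather than 87/80/80%. This stands as a caveat on the exact fit. It does not rescue the carry-over: under every loss rule tried, 24-month power exceeds the stated figures. The SAP itself ties these figures to year 1, and Study A's primary window is 12 months.

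**The figures would fit a 12-month primary window.** That is true, and a reader might infer one from the Introduction's label, "Contingency Study, Years 3-4, Niger", which stops at month 48. The Study B heading and the month-36 rerandomisation point to two years. The SAP also says that the study was extended, so a label that was not updated is the likelier explanation.

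**Nothing depends on it.** The communities already exist and the figure is conservative, so no design decision changes. This stands, and it limits the weight of the point. But the SAP presents the figures as Study B's own, not as a lower bound.

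**A stronger reading is tempting.** Item 2 names no months, and section 3 says that "the same analytic template will be used for each visit, e.g. at 48, 54, and 60 months". A reader might infer several primary tests at 0.05 and an inflated type I error. The documents do not support that. Item 2 describes a single primary analysis. Item 6 lists results by phase among additional analyses. Where the SAP wants a narrower window it says so (Study A's primary; Study B, item 5). Reporting every visit does not spend alpha. Nor does the four-year wording in the Morbidity Study paragraph bear on the mortality window, because it concerns the morbidity communities, which the protocol keeps out of the mortality comparison.

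**Conclusion.** The point holds as a misstatement of power. Study B's stated 87/80/80% describes about one year of follow-up. For months 36-60 power is about 96-97% for the 20% effect and 94-97% for the 17% and 15.5% effects. At the stated power, the detectable effects are about 16-17%, 12.5-13.4% and 11.6-12.4%.

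This rests on the Hayes-Bennett formula, an assumed loss rule (range shown), and a CV and 312 communities per arm that stay unchanged to month 60.

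The error is conservative. It does not show an underpowered study, and it endangers no conclusion. The missing months in item 2 are a gap in wording: the rest of the SAP leads to one pooled test over months 36-60.

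**What to change.** In Study B, item 1, replace the carried-over figures with power, or detectable effect, for months 36-60. State the follow-up length, formula, loss rule and number of communities used.

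Two clarifications belong in the same edit:
- Add to item 2 that the primary analysis covers months 36-60 and is tested once at two-sided 0.05.
- Update the years label in the SAP Introduction so that it covers the full extension.

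The cost is a few lines of text and a short recalculation, with no new data and no change to the analysis. No claim is given up, because by-phase results at 48 and 54 months are already non-primary under item 6.

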  - a. Analysis of the seasonality and timing of deaths: time of death, time of treatment for those who died, and time since treatment for all deaths. We will conduct comparisons of time since treatment conditional on death based on the Cramer-von Mises test (exactly as in Stage 1), additionally comparing across treatment arms and longitudinally. Comparisons of equality of circular means will be used to assess seasonality of death and of treatment, comparing between randomization arms and longitudinally. We will, in particular, focus special attention and reporting to a comparison of phases 1-4 to 5-6 within the placebo arm.
  - b. Analysis will be reported according to the same age classes used in the original study (Keenan et al, NEJM, 2018), i.e. 1-5, 6-11, 12-23, 24-59 months.
  - c. We will examine the difference between phase 5 and 6 in the same way.
  - d. We will report longitudinal analysis of mortality changes in the original azithromycin arm, using a linear predictor of study interval (1—6).
  - e. We will compare estimated treatment effect at a regional level using placebo mortality rates as a predictor.

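### Study B's primary contrast is valid and meets its stated power, but it leaves out each community's own months 0-36 mortality, a cheap and modest gain in precision

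*SAP*

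**What the plan says.** SAP Study B item 2 defines the primary analysis: "The primary prespecified analysis will contrast the rerandomized placebo arm with the rerandomized azithromycin arm". The method is negative binomial regression, two-sided at 0.05, with a permutation test by arm. No covariate is listed. Item 3 adds that "Supplementary analyses will control for prior history (original randomization arm").

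Item 1b gives the updated power: "Assuming the observed CV of 0.34, a death rate of 2% per year results in approximately 80% power to detect a 17% effect", and "A death rate of 2.5% per year (and a CV of 0.34) result in approximately 80% power to detect a 15.5% effect size". Item 1a keeps the planning case (CV 0.51, 20% effect, 312 communities per arm, about 87% power). Item 1 says these considerations are those of Study A, which lasts one year.

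Section 2 sets the timing: "At the 36 month visit, rerandomization will occur, and half of communities will begin to receive placebo". Section 3 says mortality is analysed as in Stage I, that "the same analytic template will be used for each visit, e.g. at 48, 54, and 60 months", and "Each visit that is conducted will be reported". Study A item 4e does use mortality as a predictor, but by region: "We will compare estimated treatment effect at a regional level using placebo mortality rates as a predictor".

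**The concern.** Six census intervals are complete in every continuing community before the month-36 rerandomisation. If high-mortality communities tend to stay high, that record predicts Study B deaths, and a model using it estimates the treatment effect more precisely from the same data.

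The Stage I template could not have included this covariate, because months 0-24 were then the outcome and months 24-36 had not happened. Carrying the template forward is how the baseline drops out. Original arm, the one history variable named, is not a substitute: it says which drug a community was assigned, and nothing about whether its mortality was high or low within that arm.

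At stake is some precision in the primary estimate. Bias and the type I error rate are not at issue.

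**Working it through.** **Inputs.** From Study B item 1: community size 668, 17% in the age range, 10% loss per year, 312 communities per arm, CV k = 0.34 (observed) or 0.51 (planning), death rate 2% or 2.5% per year. Person-years per community-year: 668 × 0.17 × 0.9 = 102.2. The correlation r of true community rates between months 0-36 and Study B is not in the documents. It is an assumption, shown over a range.

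**1. Reproduce the stated power.** With y person-years per community and rates λ0, λ1, the unmatched cluster-rate formula is

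z_power = √[(312 − 1)(λ0 − λ1)² / {(λ0 + λ1)/y + k²(λ0² + λ1²)}] − 1.96.

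| Case | Stated | One year | Two years |
|---|---|---|---|
| CV 0.51, 2%, 20% effect | 87% | 87.0% | 96.6% |
| CV 0.34, 2%, 17% effect | 80% | 81.9% | 96.2% |
| CV 0.34, 2.5%, 15.5% effect | 80% | 81.3% | 95.5% |

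The stated figures hold, on a one-year basis.

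**2. Variance that the prior rate can remove.** On the log scale an observed community rate has relative variance k² + 1/(expected deaths). The squared correlation between observed prior and later rates is therefore

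v = r² × reliability × share,

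where reliability = k²/(k² + 1/E_B) with E_B the deaths expected in months 0-36, and share = k²/(k² + 1/E_F) with E_F those expected in Study B.

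At CV 0.34 and 2% per year, E_B = 0.02 × 306.6 = 6.13, so reliability = 0.1156/(0.1156 + 0.1631) = 0.415. E_F = 2.04 for one year, so share = 0.191. The ceiling is 0.415 × 0.191 = 7.9%, and at r = 0.5 it is a quarter of that, 2.0%.

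| CV 0.34 | r=0.2 | r=0.3 | r=0.5 | r=0.7 | r=1 |
|---|---|---|---|---|---|
| 2%, one year | 0.3% | 0.7% | 2.0% | 3.9% | 7.9% |
| 2%, two years | 0.5% | 1.2% | 3.3% | 6.5% | 13.3% |
| 2.5%, one year | 0.4% | 1.0% | 2.7% | 5.2% | 10.7% |
| 2.5%, two years | 0.7% | 1.6% | 4.4% | 8.5% | 17.4% |

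At CV 0.51 the same formula gives 5.3-9.5% at r = 0.5 and 21-38% at r = 1.

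These values apply the control rate throughout and so run slightly high. Rates averaged over arms give 1.7-3.9% at r = 0.5 (CV 0.34), equivalent to 624 × (1/(1 − v) − 1) = about 11-25 extra communities on 624.

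**3. Effect on power at CV 0.34, r = 0.5.** One year: 81.9% to 82.6% (17% effect) and 81.3% to 82.3% (15.5% effect). Two years: 96.2% to 96.7% and 95.5% to 96.2%. Even at r = 1 the one-year values reach only 84.9% and 85.4%.

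**4. Simulated negative binomial fits** (CV 0.34, 624 communities, 12,000 trials per cell, arm alone against arm, original arm and shrunken log prior rate). Variance removed across the two rates and two windows: 1.0-4.0% at r = 0.5 and 7.6-15.7% at r = 1. At r = 0 there is a loss of 0.3-0.5%. Monte Carlo 95% half-widths are 0.2-1.3 points. The mean log rate ratio agreed between models to within 0.001. Permuting the rerandomised labels gave null rejection of 4.9% and 5.3% for the adjusted model in two settings, against 4.6% and 4.8% unadjusted.

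**5. Original arm alone (item 3).** If a 20% effect of original assignment persisted in full, arm would contribute d = (0.2/1.8)² = 0.0123 to the variance. It would remove d/(k² + 1/E_F + d), or 2.0% (2%, one year) to 3.8% (2.5%, two years), at most.

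**The case against.** The strongest case is that nothing is broken. An unadjusted randomised contrast with a permutation test is legitimate, the stated power is met, and keeping the Stage I model aids comparison across stages. Over the two years that Study B's heading covers, power is already above 95% in the updated scenarios. All of that stands, and it fixes this point as an optional improvement.

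The size rests on r, and persistence cannot be presumed: the child population is re-enumerated every six months, original placebo communities switched to azithromycin at month 24, and treatment changed again at month 36. This also stands. A reader might infer from the CV of 0.34 that community differences persist and the gain must be large. A CV describes spread between communities and says nothing about persistence.

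A reader might also infer that ignoring history biases the primary result or leaves it underpowered. The documents do not support this: rerandomisation protects the comparison, and step 1 confirms the power.

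The Stage I SAP, to which section 3 defers, is not available here. It cannot hold months 0-36 mortality as a baseline, but other covariates there could absorb part of the gain.

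Timing may be against the change. Protocol 17.8 describes the rerandomisation in the past tense, and its change-log entry is dated October 2019. The SAP reports every visit, so outcomes by arm may already be known. The documents do not settle this, and the fix allows for it.

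**Conclusion.** The point holds as a cheap improvement. Study B's primary analysis leaves unused a baseline that is already in hand. At the observed CV of 0.34, using it would remove roughly 2-4% of variance at r = 0.5 by formula (1-4% in simulated fits), or about 0.5-1 power point. The ceiling is 8-17% at r = 1. At r of 0.2 or less the effect is negligible: a gain under 1%, or a loss of up to about 0.5%. If the planning CV of 0.51 applied, the gain would be about 5-10% at r = 0.5 and 21-38% at r = 1. Everything depends on r, which is assumed, and on the SAP's planning inputs. Confidence in the size is medium.

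**What to change.** Prespecify the Study B primary as negative binomial regression on rerandomised arm, original arm, and the log of the community's months 0-36 mortality rate. Original arm belongs in the model because months 0-24 mortality carries the original treatment effect.

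To deal with zero or missing baseline deaths, shrink the rate within original arm: (D + a)/(E + a/m), where D and E are observed baseline deaths and person-time, m is the original-arm mean rate, and a is 1 over the estimated squared CV. With no baseline data this returns m. Adding a small constant to the deaths is a simpler alternative for zero counts.

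Take the p-value by permuting the rerandomised labels as allocated, with the replication rule under Statistical considerations item 3 unchanged. Keep the unadjusted Stage I-template model as a sensitivity analysis.

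Do not make adjustment conditional on an estimate of r. Comparing months 0-24 with months 24-36 gives a standard error of √[(k² + 1/4.09)(k² + 1/2.04)/624]/k² = 0.16. Against a threshold of 0.2, the decision would go the wrong way about 27% of the time at a true r of 0.1 or 0.3, and the primary model would become data-dependent.

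Enter the change in the SAP change log before any Study B outcome by arm is seen. If such outcomes have been seen, leave the primary as it is and report the adjusted model as a labelled secondary analysis.

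Cost: a short amendment, a shrinkage step, slightly less direct comparability with Stage I, and up to about 0.5% of variance if prior mortality is uninformative. No new data are needed.
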